IVFE reduction (IFER) during the administration of neonatal parenteral nutrition will lead to a significant decrease in the rate of rise of direct bilirubin (mg/dL/week) when compared to standard therapy.

Secondary Hypotheses

1. The time to development of PNAC, when present, will be longer with IFER when compared to standard IVFE therapy.
2. IFER will not be associated with a significant increase in failure to thrive (as assessed by growth parameters) or the development of essential fatty acid deficiency (EFAD) when compared to standard IVFE therapy.
3. Neurodevelopmental outcomes (NDOs), when assessed at 12 and 24 months of corrected gestational age, will be similar for those treated with IFER and standard IVFE therapy.

Specific Aims

1. To determine whether neonates and infants receiving PN with IFER (1 g/kg/day) will have lower rates of rise of direct bilirubin compared to those receiving standard IVFE therapy (3 g/kg/day)
2. To compare the time to development of PNAC in neonates and infants receiving PN with IFER (1 g/kg/day) compared to those receiving PN with standard IVFE administration (3 g/kg/day)
3. To determine if IFER results in normal growth and essential fatty acid (EFA) parameters by measuring weight, length, head circumference (weekly) and EFA profiles (every 2 weeks in the IFER group) during the treatment period.
4. To compare NDOs at 12 and 24 months of corrected gestational (± 2 weeks) age of those treated with IFER with those treated with standard IVFE doses using a combination of neurodevelopmental screening tools (e.g. Bayley Scales of Infant Development, MacArthur Communicative Development Inventory, etc.) aimed at capturing several developmental domains such as motor, cognition, speech and language, sensory, and behavior.

Study Definitions

Subjects will be considered “on treatment” from the time of randomization until 7 days after PN has been discontinued, but not to exceed a total of 84 days. Subjects will be considered “on study” until they complete their neurodevelopmental testing at 24 months corrected gestational age (± 2 weeks).

Study Design

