This is a multi-institution, prospective, randomized study evaluating IVFE dose reduction on the development of PNAC as a proxy measure of PNALD in neonates requiring prolonged PN. The definition of PNAC will be that used predominantly in the literature – a direct bilirubin level of ≥ 2 mg/dL, documented on two occasions 1 week apart, in patients who have required parenteral nutrition for more than 2 weeks. **Eligible neonates will be randomized into two treatment arms: standard IVFE administration (3 g/kg/day) or IVFE reduction (IFER) (1 g/kg/day).** A total of 60 subjects (30 subjects per arm) will be included in the study. The study will evaluate

short- and long-term outcomes of this strategy. In the short-term, infants will be followed for up to 12 weeks for the development of PNAC. If a subject's PN is discontinued before 12 weeks, and if they remain in the hospital, follow-up data will be collected for an additional 7 days but not beyond a total of 84 days. Only standard-of-care data will be collected during these 7 days. No procedures will be performed for the purpose of this study during these 7 days. In the long-term, subjects' neurodevelopmental outcomes will be assessed at 12 and 24 months corrected gestational age (± 2 weeks).

Primary outcome measure:

1. The rate of rise of direct bilirubin as a function of time (mg/dL/week) between the two groups over 12 weeks or until the subject has been off of PN for >7 days, whichever comes first.

Secondary outcome measures

1. Initial 12 week period:
 - a. The incidence of PNAC (direct bilirubin ≥ 2 mg/dL) and severe PNAC (direct bilirubin ≥ 4 mg/dL in subjects on parenteral nutrition for at least 2 weeks)
 - b. The time to development of PNAC and severe PNAC
 - c. The peak total and direct bilirubin levels
 - d. The incidence of EFAD
 - e. Adequacy of growth as evaluated by z-scores for weight, height, and head circumference
 - f. Other safety measures assessed during the initial 12 week period will include adverse events (e.g., episodes of sepsis and catheter-related blood stream infections).
2. Long-term follow-up:

Neurodevelopmental assessments will include:

 - a. At 12 months corrected gestational age (± 2 weeks):
 - i. Bayley Scales for Infant and Toddler Development (BSID-III)
 - b. At 24 months corrected gestational age (± 2 weeks):
 - i. Bayley Scales for Infant and Toddler Development (BSID-III)
 - ii. MacArthur-Bates Communicative Development Inventories (CDI)

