3. Weight, gestational age at the time of enrollment/randomization, and weekly thereafter
4. Inclusion diagnosis
5. Number of septic episodes according to standard definitions³⁸
6. Use of choleric medications
 - a. Ursodiol
 - b. Cholecystokinin
 - c. Phenobarbital
7. Nutritional data
 - a. Parenteral nutrition data
 - i. IVFE dose
 - ii. Dextrose infusion rate
 - iii. Total calories and % calories obtained via PN
 - b. Enteral nutrition data
 - i. Total calories and % calories being obtained via enteral route
 - ii. % calories obtained via breast milk
8. Growth parameters (whenever possible, obtain all growth measurements on the same day of the week)
 - i. Weight (with z-score) weekly (every 7 days ± 2 days)
 - ii. Height (with z-score) weekly (every 7 days ± 2 days)
 - iii. Head circumference (with z-score) weekly (every 7 days ± 2 days)
9. Additional safety data to be obtained from human subjects is summarized below, indicating any key differences in frequency of monitoring between the two groups:

Laboratory Parameter	Frequency (+24 hours)*
Fractionated bilirubin panel (includes total, indirect, and direct bilirubin)	One time weekly (Monday)
Serum bile acids (total)	One time monthly (every 4 th Monday on treatment)

Point of care or serum glucose measures	- Daily for the first 5 days of PN, then twice weekly (Monday, Thursday) - Confirmatory test if serum glucose is >150 mg/dL on electrolyte panel
Serum Triglycerides	One time weekly (Monday)
Essential Fatty Acid Profile	IFER Group: Every 2 weeks (Thursday) Standard Group: At the time of restriction of IVFE to 1 g/kg/day three days per week, then every 2 weeks (Thursday)
Comprehensive metabolic panel	Twice weekly (Monday, Thursday)
Magnesium level	Twice weekly (Monday, Thursday)
Phosphorus level	Twice weekly (Monday, Thursday)
Complete blood count	One time weekly (Monday)

* Lab draw volumes will be below each institution's daily limits

Definition of Sepsis

Sepsis will be defined in a standard manner using the following criteria (**Table 2**):³⁸

The presence of at least two of the following four criteria ***in the presence of or as a result of suspected or proven infection***:

1. Core temperature of >38.5C or <36C

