All adverse events will be graded as follows in their relation to IFER: definitely not related, unlikely to be related, possibly related, definitely related or insufficient information. All cases rated as possibly or definitely related will be defined as an SAE. These SAEs will be reported to the University of Michigan Sponsor-Investigator within 48 hours. The site PI will be contacted immediately and the case will be evaluated for reporting to IRB, FDA and study termination, if deemed necessary. Each clinical site will report SAEs to their local IRB as per their standard reporting policy. As per 21 CFR 312.32(c), the sponsors will also notify FDA and all participating investigators in an IND safety report of any adverse experience associated with the use of the drug that is both serious and unexpected.

Data Safety Monitoring Board

An independent data safety monitoring committee will be established to monitor the study for safety and to determine if a statistical difference has been achieved between the two groups for the primary outcome measure at interim data analyses. The data safety monitoring committee will review the data at the halfway point of the study to assess the safety and efficacy of the study to that point. If safety issues are revealed the study investigators and each site's IRB will be notified immediately. The data safety monitoring committee will also ensure that adverse events are promptly reported to the FDA, and all participating investigators will be notified as well of any adverse experience associated with the use of the drug that is both serious and unexpected.

Sample Size Determination

The sample size was calculated for the primary outcome (rate of rise of direct bilirubin) using previously published data as well as our clinical experience.^{22,23} We have assumed that the mean bilirubin levels at baseline, 4 weeks, 8 weeks and 12 weeks in the standard dosing group (2-3 g/kg/day) will be 0.55 mg/dL, 1 mg/dL, 1.5 mg/dL and 2 mg/dL corresponding to a slope of 0.125 mg/dL/week over 12 weeks. The standard deviation of the bilirubin measures at each of these four time points is 1. Likewise, we have estimated that the mean bilirubin levels at baseline, 4 weeks, 8 weeks and 12 weeks in the minimization group (1 g/kg/day) will be 0.45 mg/dL, 0.5 mg/dL, 0.45 mg/dL and 0.5 mg/dL (a slope of roughly zero). The standard deviation of the bilirubin measurements at

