Descriptive statistics using standard statistical tests (e.g. Student's t-test, paired sample t-test, Wilcoxon rank sums tests, Fisher's exact tests, Chi-square test, McNemar's test, etc.) will be used throughout the statistical analysis of data. Logistic regression will be used to compare differences between groups. Because septicemia can exacerbate PNAC, we will include the incidence of septicemia as a covariate in our analysis. Septic episodes will be defined as positive cultures or clinical presentation consistent with sepsis during the 7 day period corresponding to the subject's weekly bilirubin value. The number of septic episodes will be accounted for using a Poisson regression analysis (or possibly a negative binomial regression if there is more variability than expected for a Poisson distribution), with the total time on PN as an offset, allowing us to compare the rate of occurrence of septic episodes in the two groups.

Primary Outcome Measure

The primary outcome measure – change in direct bilirubin as a function of time (mg/dL/week) between the two groups – will be evaluated using a linear mixed model analysis to compare the slope of total bilirubin levels between the standard and reduced groups. This model will allow us to examine the degree of variability between subjects in the rate of change over time, and will take this variability into account in the model by including a random effect for the slope of time for each subject as well as a random intercept for each subject.

Secondary Outcome Measures

1. Time to PNAC (direct bilirubin ≥ 2 mg/dL) and time to severe PNAC (direct bilirubin ≥ 4 mg/dL)

The time to development of a first occurrence of PNAC and of severe PNAC will be evaluated using survival analysis. Initially, we will compare the two groups using Kaplan-Meier curves, but the eventual analysis will take into account important covariates, such as development of sepsis, average IVFE dose and percentage of calories from enteral feeds using a Cox proportional hazards survival analysis. We will test whether the proportional hazards assumption is met for the analysis by including an interaction term between treatment group and time to see if any differences between the groups are consistent or increase/decrease over time. The effect of important time-varying covariates (e.g., septic episodes) can also be taken into account using a Cox model.

2. Level of peak total and direct bilirubin

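### The sentence that specifies the primary analysis names direct bilirubin as the outcome but fits the model to total bilirubin

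*Combined protocol and SAP*

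**What the plan says.** The primary analysis is specified in one sentence, under Planned Statistical Analysis, Primary Outcome Measure. It opens by naming the outcome as "change in direct bilirubin as a function of time (mg/dL/week) between the two groups" and goes on to say that this outcome "will be evaluated using a linear mixed model analysis to compare the slope of total bilirubin levels between the standard and reduced groups". The sentence after it adds a random intercept and a random slope for each subject but does not name the response variable.

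Everything upstream of that sentence refers to direct bilirubin:

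- Primary Hypothesis: lipid reduction "will lead to a significant decrease in the rate of rise of direct bilirubin (mg/dL/week) when compared to standard therapy". Specific Aim 1 is framed the same way.
- Study Design, Primary outcome measure: the endpoint is given as "The rate of rise of direct bilirubin as a function of time (mg/dL/week) between the two groups over 12 weeks", with an earlier end for infants more than 7 days off parenteral nutrition.
- Sample Size Determination: its opening sentence ties the calculation to the rate of rise of direct bilirubin.

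The document treats direct and total bilirubin as separate quantities. The laboratory table in Data Collection lists a weekly fractionated panel that reports total, indirect and direct values, and item 2 of the secondary outcomes is headed "Level of peak total and direct bilirubin".

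**The concern.** A statistician programs from the analysis section. Total bilirubin will be in the dataset for every weekly draw, so a model written to the letter of this sentence would run without any error or warning. It would estimate a treatment difference in a quantity that includes indirect bilirubin, whereas the hypothesis, the endpoint definition and the cholestasis definitions all rest on the direct fraction.

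Left as it is, the plan supports two different primary analyses. The direct-bilirubin slope can be defended from the outcome definition, and the total-bilirubin slope from the model sentence. If the two disagreed, the choice would be made after the data were seen, which is what prespecifying the primary variable is meant to prevent.

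The same ambiguity reaches the halfway review. Under Data Safety Monitoring Board, the committee is "to determine if a statistical difference has been achieved between the two groups for the primary outcome measure at interim data analyses". If the committee's statistician takes the model from the analysis section, that look could be at the wrong variable.

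**Working it through.** **Step 1. Compare the statements on the primary variable.**

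| Place in the document | Variable |
|---|---|
| Primary Hypothesis | direct |
| Specific Aims, item 1 | direct |
| Study Design, Primary outcome measure | direct |
| Sample Size Determination, opening sentence | direct |
| Primary Outcome Measure paragraph, start of sentence | direct |
| Primary Outcome Measure paragraph, model clause | **total** |

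Five statements agree and one does not. The one that differs is the only one that says what the model is fitted to. Sample Size Determination mentions a repeated measures ANOVA, but as the basis for power, not as the planned analysis, so it does not replace the model clause.

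**Step 2. Confirm that the stated power belongs to direct bilirubin.** Inputs, all from Sample Size Determination:

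- means at weeks 0, 4, 8 and 12 of 0.55, 1, 1.5, 2 mg/dL (standard) and 0.45, 0.5, 0.45, 0.5 mg/dL (reduced)
- SD 1 at each time
- correlations 0.5, 0.354 and 0.25 at lags of 4, 8 and 12 weeks
- significance level 0.05 (taken as two-sided; the document does not say)

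Repeated measures ANOVA with the Geisser–Greenhouse adjustment (noncentral F approximation) for the slope and time tests, and noncentral t for the group means:

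| Per group | Slopes: stated / recomputed | Group means: stated / recomputed | Time: stated / recomputed |
|---|---|---|---|
| 15 | 85% / 86.0% | 79% / 79.6% | 88% / 88.9% |
| 20 | 95% / 95.1% | 90% / 90.2% | 96% / 96.5% |

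Attrition: 20 / (1 − 0.33) = 29.9, so 30 per group, as stated. The plan's figures hold for direct bilirubin.

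**Step 3. Slope difference and its SD.** The least-squares slope over the four times uses weights (−6, −2, 2, 6)/80.

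- Standard: (−3.3 − 2 + 3 + 12)/80 = 9.7/80 = 0.1213 mg/dL/week
- Reduced: (−2.7 − 1 + 0.9 + 3)/80 = 0.2/80 = 0.0025 mg/dL/week
- Difference: 0.1188 mg/dL/week
- Variance of one subject's slope: [80 + 2(20)(0.5) + 2(−24)(0.354) + 2(−36)(0.25)]/6400 = 65.008/6400 = 0.01016, so SD 0.1008

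The document's 0.125 for the standard arm is 0.121 on its own means. This has no bearing on the point here.

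The two-sample t-test on slopes has noncentrality 0.1188 / (0.1008 × √(2/n)). At n = 20 this is 3.73. Power is 87.6%, 95.3% and 99.4% at 15, 20 and 30 per arm. The figure at 15 exceeds the plan's 85% because this is a different test from the ANOVA.

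**Step 4. Illustration for total bilirubin.** The document gives no mean, SD or correlation for total or indirect bilirubin, so this step rests on assumptions. Suppose the indirect fraction adds independent slope noise with SD equal to k times the direct slope SD, and carries no treatment effect. The slope SD is then multiplied by √(1 + k²), and the correlation between total and direct slopes is 1/√(1 + k²).

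| k (assumed) | Implied correlation | Power at 15 per arm | at 20 | at 30, complete data |
|---|---|---|---|---|
| 0 (direct) | 1 | 87.6% | 95.3% | 99.4% |
| 0.33 | 0.95 | 84.1% | 93.2% | 98.9% |
| 0.5 | 0.89 | 79.6% | 90.1% | 98.0% |
| 1 | 0.71 | 59.6% | 72.8% | 88.7% |

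The column for 30 is an upper bound, since the plan allows for 33% attrition. The neurodevelopmental analysis text expects total and direct bilirubin to be strongly collinear. That fits the k = 0.33 and 0.5 rows better than k = 1, which is shown only as an extreme.

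**The case against.** The strongest reply is that this is a self-evident slip. The intended variable can be recovered from the hypothesis, Aim 1, the outcome definition, the sample size section and the subject of the disputed sentence itself, and no part of the document proposes total bilirubin as a primary outcome. A statistician who read the whole protocol would very likely analyse direct bilirubin. This is right about intent. It does not remove the problem, because the wrong word sits in the only sentence that defines the confirmatory model and would still be available to justify an analysis of total bilirubin.

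Three narrower objections also have force:

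- The halfway review refers to the primary outcome measure, which Study Design defines as direct bilirubin. The model sentence therefore makes the variable for that look ambiguous; it does not settle it.
- The power illustration uses invented inputs, and assuming independent noise with no treatment effect guarantees a loss. It should carry no weight in judging how serious the point is.
- The expected collinearity suggests that the practical difference may be small. That remark, however, concerns which of the two to use as a covariate in the neurodevelopmental models. It does not make total bilirubin an acceptable substitute for the primary endpoint.

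**Conclusion.** The point holds. The primary analysis sentence contradicts itself and the rest of the document, and no other text corrects it. This conclusion comes from reading the document and needs no assumption.

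The consequence is that the confirmatory test, as written, addresses an undeclared endpoint. Any loss of power is secondary and cannot be determined from the document. On the more plausible assumed values it is about 2 to 5 percentage points at 20 per arm and at most about 1.5 points at 30 per arm with complete data. The correction is needed because the sentence governs the primary test, even though the intended reading is clear.

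**What to change.** In Planned Statistical Analysis, Primary Outcome Measure, change the model clause so that it compares the slope of *direct* bilirubin between the arms. For clarity, add that the primary test is the treatment-by-time coefficient in that model, and that any analysis of the total-bilirubin slope is secondary. Leave the planned comparison of peak total and peak direct bilirubin as it is.

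The essential change is one word; the added statements take a sentence or two. No new data are needed, and the sample size and stated power stand. The correction should be made before any analysis of the primary outcome, including the halfway review.

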 - iii. Brief Infant Toddler Social Emotional Assessment (BITSEA)
 - iv. Gross Motor Function Classification System (GMFCS)
 - v. Behavioral Assessment System for Children-Second Edition (BASC2)

Study Arms:

[figure not shown]
Study Arm 1 (Standard IVFE dosing): Subjects in the standard IVFE dosing arm (3 g/kg/day) will be on treatment for a total of 12 weeks or until the subject has been off of parenteral nutrition for >7 days, or if they are discharged from the hospital, whichever comes first.

Study Arm 2 (IFER dosing): Subjects in the IFER dosing arm (1 g/kg/day) will be on treatment for a total of 12 weeks or until the subject has been off parenteral nutrition for >7 days, or if they are discharged from the hospital, whichever comes first.

All subjects will be maintained at their assigned dosing regimen for the duration of the treatment period (12 weeks) or until they are transitioned off of PN for >7 days, are discharged or until the direct bilirubin is ≥ 2.5 mg/dL for 2 consecutive weeks, whichever occurs first. Data will be collected for the duration of the study for those subjects who remain on parenteral nutrition for the full 12 weeks. For those who transition off of PN prior to the end of the 12 week period, data will be collected for 7 days after termination of PN if the subject remains in the hospital. The clinical course of these subjects who wean off PN prior to 12 weeks will continue to be monitored according to standards of practice. If serum direct bilirubin reaches a level of ≥ 2.5 mg/dL for 2 consecutive weeks during the course of the treatment, subjects will be transitioned to an IVFE dose of 1 g/kg/day three days per week. Those who remain cholestatic at the termination of their treatment period will be evaluated on a monthly basis for the persistence or resolution of cholestasis. This will be done by obtaining monthly liver function tests and bilirubin fractions for 6 months.

Overview of Study Design:

Study Design

Inclusion Criteria

Study subjects will be neonates and infants who are ≥ 28 weeks corrected gestational age at the time of enrollment who are parenteral nutrition naïve (<72 hours of PN exposure prior to randomization) and whose direct bilirubin has never been >2 mg/dL with at least one of the following diagnoses:

1. Meconium ileus and peritonitis
2. Gastroschisis
3. Omphalocele >4 cm in diameter or with liver herniated outside of the abdominal cavity

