each of these four time points is 1. The correlation of any two adjacent measures on the same individual is 0.5. This correlation drops to 0.354 between baseline and 8 weeks and to 0.25 between baseline and 12 weeks.

Using the above assumptions, a sample size of 15 subjects per group using a repeated measures ANOVA will have 85% power to detect the change in slopes as being significant at the 0.05 level, 79% power to detect a difference in means overall between groups and 88% power to detect the general change in means over time across the two groups. When the sample size is increased to 20 subjects per group, the above power numbers increase to 95%, 90% and 96%, respectively. If 30 subjects are recruited per group this design will allow for a 33% attrition rate by twelve weeks as we expect that not all patients will require PN for the full 12 weeks of the initial study period. Thus, we will recruit a minimum of 30 subjects per group to ensure adequate power to detect our primary outcome measure.

Of the secondary outcomes, sample size was also calculated for the incidence of cholestasis. Assuming an incidence of 50% in the standard group and an incidence of 10% in the minimization group, with $\alpha = 0.05$ and power of 80%, a sample size of 23 is required for each group. Regarding the other secondary outcomes, our sample size is large enough to allow for establishing trends which may then highlight avenues for future research.

Planned Statistical Analysis

All data analysis will be directed and performed by a statistician through the Center for Statistical Consultation and Research at the University of Michigan (<http://cscar.research.umich.edu/about/>). Data will be analyzed using SAS software release 9.3 for Windows (Copyright, SAS Institute Inc., SAS and all other SAS Institute Inc. product of service names are registered trademarks or trademarks of SAS Institute Inc., Cary, NC, USA). All study subjects will be included in the statistical analysis in an intent-to-treat manner.

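### If infants weaned off PN are censored, the planned Kaplan-Meier curves for time to PNAC overstate the 12-week risk within each arm; cumulative incidence should replace them

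*Combined protocol and SAP*

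**What the plan says.** All references are to the combined protocol and SAP.

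- **Secondary Outcome Measures, item 1 (analysis section).** Time to first PNAC and time to first severe PNAC are analysed by survival methods: "Initially, we will compare the two groups using Kaplan-Meier curves". The later analysis adjusts for sepsis, average lipid dose and "percentage of calories from enteral feeds using a Cox proportional hazards survival analysis".
- **Study Design.** PNAC needs a direct bilirubin of at least 2 mg/dL on two occasions a week apart, "in patients who have required parenteral nutrition for more than 2 weeks". For this outcome "infants will be followed for up to 12 weeks for the development of PNAC".
- **Study Arms.** For infants who come off PN before week 12, "data will be collected for 7 days after termination of PN if the subject remains in the hospital".
- **Sample Size Determination.** With 30 infants in each arm, "this design will allow for a 33% attrition rate by twelve weeks as we expect that not all patients will require PN" up to week 12. For PNAC incidence the text reads "Assuming an incidence of 50% in the standard group and an incidence of 10% in the minimization group".

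The document has no censoring rule for weaning, discharge, death or study exit in this analysis. It mentions neither competing risks nor cumulative incidence, and it gives no weaning rate by arm.

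**The concern.** An infant who comes off PN leaves the process that produces PNAC and, within a week, leaves the data as well. Death ends the risk outright. Neither is ordinary loss to follow-up.

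If weaned infants are censored, Kaplan-Meier drops them from the risk set and assumes that their later hazard of PNAC would have matched that of infants still on PN. The plan contradicts this assumption: under Potential Confounding Variables it says that infants who tolerate even small enteral volumes have a lower risk than those fully dependent on PN. 1-KM then describes a setting in which no infant is ever weaned or dies, not the share of randomized infants who develop PNAC by week 12.

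This matters because the Kaplan-Meier curve is the only named time-to-event display of absolute risk. The Cox model gives a hazard ratio, and the incidence analysis (item 3) gives a rate per time on PN. Readers will take the week-12 height of the curves as the risk of PNAC, and the gap between them as the absolute benefit.

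**Working it through.** **Plan's own figures.** No stated number rests on the Kaplan-Meier curves. The two figures used as inputs below do reproduce:
- 50% vs 10%, alpha 0.05 (two-sided assumed), Fisher exact test: power is 78.6% with 22 per group and 81.1% with 23, so the stated 23 per group is right.
- 20 / (1 - 0.33) = 29.9, so 30 per group. The 33% is the margin between 30 recruited and the 20 used in the power calculation.

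**Assumptions.** Cause-specific hazards are constant over 12 weeks, and weaning is the only competing event. The weaning shares are assumed; 33% is borrowed from the attrition allowance.

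**Reading A: 50% and 10% are the true incidences.** Let p be the share with PNAC and w the share weaned first.
- Total cumulative hazard H = -ln(1 - p - w)
- PNAC part = H × p / (p + w)
- 1-KM = 1 - exp(-PNAC part)

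With w = 0.33 in both arms:
- Standard: H = -ln(0.17) = 1.772; × 0.50/0.83 = 1.067; 1-KM = 65.6%.
- IFER: H = -ln(0.57) = 0.562; × 0.10/0.43 = 0.131; 1-KM = 12.3%.
- Gap: 53 points, against a true 40.

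With w = 0.20 in both arms, 1-KM is 57.7% vs 11.2%, a gap of 46 points.

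**Reading B: 50% and 10% are 1-KM values.** Here 33% is the chance of weaning by week 12 if PNAC did not intervene.
- A = -ln(1 - risk); B = -ln(1 - 0.33) = 0.400
- Cumulative incidence = A/(A + B) × (1 - exp(-(A + B)))
- Standard: A = 0.693; 0.634 × 0.665 = 42.1%.
- IFER: A = 0.105; 0.208 × 0.397 = 8.3%.
- Gap: 34 points, against 40 on the curves. With 50% weaning in both arms the true gap is 30.2 points.

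**Direction of the bias between arms.** The Background cites a retrospective study with 43% on standard dosing and 22% on reduced dosing. Take these as true incidences (reading A formulas):

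| Weaned first, standard / IFER | 1-KM, standard vs IFER | Gap on the curves | True gap |
|---|---|---|---|
| 33% / 33% | 55.4% vs 27.3% | 28.1 | 21 |
| 30% / 60% | 53.8% vs 36.9% | 16.9 | 21 |

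In the second row: standard, -ln(0.27) × 0.43/0.73 = 0.771; IFER, -ln(0.18) × 0.22/0.82 = 0.460. Within each arm the curve is too high in both rows, but the gap is too wide in the first and too narrow in the second.

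**Hazard ratio.** Under reading B it is ln(0.9)/ln(0.5) = 0.152 whatever the weaning share, because B does not enter.

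**The case against.** The case against has five parts.

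- **The curves are only a first look.** The main analysis is the Cox model. With weaned infants censored it estimates a cause-specific hazard ratio, which this mechanism does not inflate. This stands and limits the importance of the point.
- **A reader might infer that Kaplan-Meier keeps weaned infants at risk.** It does not. Censored infants leave the risk set. In a simulation of reading B (weaning one third), keeping them in the risk set to week 12 gave 42.2% and 8.3%, matching the cumulative incidence. The overstatement comes from censoring them, and the plan implies that step without stating it.
- **A reader might infer that the benefit of lipid reduction is bound to look too large.** The documents do not support this, because they give no weaning rate by arm and the second row of the table goes the other way. That reversal needs clearly faster weaning on IFER.
- **A reader might take 33% as a forecast of weaning, or 40 points as the true difference.** The first is a sample-size allowance: the plan expects only that some infants will not need 12 weeks of PN. For the second, the plan does not say whether 50% and 10% are crude proportions or Kaplan-Meier risks. Hence the two readings.
- **A reader might expect the curves to contradict the incidence outcome.** That outcome is analysed as a rate with time on PN as offset, so it is not a 12-week proportion to set directly against the curves.

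None of this removes the within-arm overstatement if weaned infants are censored.

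**Conclusion.** The point holds for the displayed absolute risks. If weaned infants are censored, 1-KM overstates the 12-week risk of PNAC in each arm. With 33% weaned in each arm and constant hazards, the overstatement on standard dosing is about 16 points under reading A (66% vs 50%) and 8 under reading B (50% vs 42%). On IFER it is about 2 points under either reading. The gap between arms is then too wide by about 13 or 6 points. With unequal weaning it could instead be too narrow, so the direction of that bias cannot be settled from the documents.

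The cause-specific hazard ratio, the primary outcome and the sample size are not affected. This is an inexpensive improvement to a named secondary outcome and does not threaten the trial's main conclusion.

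**What to change.** In Secondary Outcome Measures, item 1:

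1. Replace the Kaplan-Meier display with Aalen-Johansen cumulative incidence of PNAC and of severe PNAC by arm, with 95% confidence intervals.
2. Treat end of PN and death as competing events. Count PNAC that arises in the 7 days after PN ends wherever it is observed. An infant weaned and discharged within those 7 days should be classed as weaned, not censored.
3. Treat discharge on PN, transfer to a non-study hospital and growth-failure exit as censoring, and report the number of each by arm. The growth-failure exit sits in a section headed for the lipid-restricted group only, so this censoring may differ between arms.
4. Keep the Cox model and label its result a cause-specific hazard ratio. Gray's test is optional: it compares cumulative incidence and so mixes effects on weaning with effects on PNAC.

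**Cost.** SAP wording and a few lines of code. Time on PN is already needed for the offset in the incidence analysis, and deaths are recorded. The displayed risks will be lower than Kaplan-Meier would show. Cumulative incidence also reflects any effect of treatment on weaning, so weaning should be shown by arm beside it.
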